1.1 Objective of the Updated Statistical Analysis Plan

The objective of this updated statistical analysis plan (SAP) is to provide a description of the updated analytic strategy and the statistical methods that will be used to analyze the data for the Program for Lung cancer screening and Tobacco cessation (PLUTO) Trial which uses a sequential multiple assignment randomized trial (SMART) design. The primary objective of the trial is to determine among incomplete responders to first stage tobacco longitudinal care (TLC) if medication therapy management (MTM) added to TLC is an effective approach for long-term tobacco cessation compared to TLC alone. The primary endpoint of this trial is a binary outcome of long-term tobacco cessation assessed 18 months after initial tobacco cessation treatment.

The primary statistical analysis plan was described in detail in the protocol paper (Fu et al., *Contemporary Clinical Trials*¹). However, changes to the protocol and study status have necessitated updating the statistical analysis plan.

This updated SAP was prepared prior to unblinding of the data by statisticians and other members of the core PLUTO team who have been blinded to interim treatment comparisons for the duration of the trial.

Below we briefly summarize the status of the trial and some key blinded data that informed the preparation of this updated SAP.

1.2 Trial Status and Information That Informed the Updated SAP

1.2.1 Trial Status

The protocol underwent a number of minor changes throughout the study. Two key changes to the protocol are described below.

When the trial opened, participants were required to be scheduled for or have an order for first-time low dose CT for lung cancer screening. Due to fewer people undergoing lung cancer screening (both within the health systems studied in this trial and nationwide), we expanded the inclusion criteria. Eligibility was first expanded in January 2017 at the University of Minnesota and Minneapolis VA to include patients receiving repeat low dose CT for lung cancer screening, in addition to patients receiving first time scans. To further increase enrollment, we added a new site, Allina Health, in June 2018. In September 2018, criteria at the University of Minnesota (UMN) site were expanded to include all people who smoke who were eligible for lung cancer screening on the basis of their age and smoking history. Similarly, the criteria were expanded at the Minneapolis VA to include those who were eligible for lung cancer screening and a part of the lung cancer screening program regardless of their intention to receive another lung cancer screening.

Due to the COVID-19 pandemic-related safety protocols, saliva was no longer collected from participants after March 23, 2020. Thus, cotinine verification of smoking cessation was not able to be assessed after this date. From March 23, 2020 until May 19, 2020,

no participants were sent any biochemical verification. Beginning on May 19, 2020, participants were sent an iCO smokerlyzer to verify abstinence. Additionally, we attempted to send the iCO smokerlyzer to participants to whom we could not send a saliva kit from March 23, 2020 until May 19, 2020 even if those the data collection for those participants was out of window. We paused sending iCO smokerlyzers from July 2020 to December 2020 due to limited product availability.

1.2.2 Enrolment Summary

The first participant was enrolled on November 11, 2016; the last participant was enrolled on September 25, 2019. A total of 691 participants were enrolled across the three sites. Thirty-one participants withdrew prior to the baseline visits, and an additional 17 participants did not complete the outreach call after the baseline visit; thus, 643 participants were randomized to 4- or 8-week assessment of first stage TLC. A total of 510 participants were incomplete responders and were randomized to TLC vs. TLC + MTM; 126 participants were complete responders and randomized to TLC-Q vs. TLC-M. Seven participants were not randomized a second time. Thus, a total of 636 participants were randomized twice.

1.2.3 Summary of Pooled (Both Treatment Groups Combined) Follow-up Results

The final data collection was completed on May 1, 2021. Table 1 describes the data available from the Week 52 and Week 78 data collection calls. In general, data on abstinence is available if the participant only completed a mail-in survey (other secondary measures are not available). Among participants still alive, data are available on 86.8% (547/630) and 84.6% (529/625) of participants at Week 52 and Week 78.

Tables 2 and 3 summarize the number of participants randomized to each condition and the pooled (blinded), self-reported long-term abstinence.

Table 1: Data availability at Week 52 and 78 data collection calls.

Status at data collection call	Week 52 n=	Week 78 n=
Complete	517	494
Missed	63	77
Incomplete	0	0
Participant withdrew from study	15	16
Participant refused call	5	3
Participant only did mail-in survey	30	35
Death on study	6	11
Total	636	636

Table 2: Number of participants randomized to each condition

Complete responder n=126				Incomplete responder n=510			
Week 4		Week 8		Week 4		Week 8	
TLC_M	TLC-Q	TLC_M	TLC-Q	TLC-M	MTM	TLC-M	MTM
n=32	n=34	n=32	n=28	n=133	n=120	n=123	n=134

Table 3: Pooled smoking outcomes at Week 52 and 78.

Smoking outcomes	Week 52 n=	Week 78 n=
1) Smoked in past 7 days;		
No	187 (34.3%)	191 (36.1%)
Yes	359 (65.8%)	338 (63.9%)
Missing	90	107
2) Smoked in the last 30 days:		
No	166 (77.9%)	169 (78.2%)
Yes	47 (22.1%)	47 (21.8%)
Missing*	423	420
3) Smoked 7 consecutive days in last 6 months;		
No	123 (64.7%)	131 (67.9%)
Yes	67 (35.3%)	62 (32.1%)
Missing*	446	443
4) Smoked in 2 consecutive weeks in last 6 months:		
No	115 (79.3%)	130 (83.3%)
Yes	30 (20.7%)	26 (16.7%)
Missing*	491	480
Prolong abstinence (#1, #3, and #4 =No)	113/636 (17.8%)	129/636 (20.3%)

1.2.4 Sample Size Re-Estimation

In April 2019, the blinded statisticians were provided the pooled (both treatment groups combined) proportions of complete and incomplete responders and the proportion of those achieve long-term abstinence among incomplete responders in order to re-estimate sample size. Based on the observed pooled proportions, we estimated between 75-80% of the sample would be incomplete responders and of those incomplete responders between 10-15% would achieve long-term abstinence with TLC alone. The protocol paper outlines that we designed the study to have at least 80% power to detect a risk difference of 10 percentage points. Table 4 outlines the power for the primary aim under these assumptions. Based on these data, we changed the planned enrollment from 1,000 to 700.

Table 4: Power estimates based on updated observed pooled proportions of the proportions of incomplete responders and proportion of incomplete responders achieving long-term abstinence.

n=700					
Proportion incomplete responders=80%			Proportion incomplete responders=75%		
	TLC achieving long-term abstinence			TLC achieving long-term abstinence	
TLC+MTM long-term abstinence	10%	15%	TLC+MTM long-term abstinence	10%	15%
7.5% diff	73%	62%	7.5% diff	70%	60%
10% diff	91%	84%	10% diff	90%	82%

1.3 Summary of Changes to SAP

Based on the above information and additional data expected we made the following changes and clarifications to the SAP:

1. *Change in primary outcome:* Because saliva samples could not be collected for a portion of the sample due to COVID-19, biochemical verification could not be completed for all those self-reporting long-term abstinence. The primary outcome will be self-reported long-term abstinence at 78 weeks (18 months). This is defined as not smoking at all (even a puff) for the past 7 days and not smoking for 7 consecutive days during the past 6 months. As a supportive analysis, we will impute the missing biochemical verification data on those self-reporting long-term abstinence who declined biochemical verification, did not return the saliva/iCO smokerlyzer kits, or who were not sent a kit in window.
2. Adjusted analysis for primary and secondary aim: The enrolment for the trial was lower than anticipated. In particular, we initially anticipated between 650 and 750 incomplete responders whose outcomes would inform the analysis for the primary outcome. Based on the sample size re-estimation we anticipated between 525 and 560 incomplete responders. A total of 510 incomplete responders were randomized to second stage treatment. Similarly, initial power calculations assumed that there would be between 250 and 350 complete responders but only 126 participants were complete responders in this trial. In general, our other assumptions for the power calculations (e.g., long-term abstinence rate in the control group) were reasonable. To account for the under-enrolment, the primary analysis for the primary aim (comparison of TLC+MTM vs. TLC for incomplete responders) and secondary aim 1 (comparison of TLC-Q vs TLC-M) will be a logistic regression model with covariates for age, cigarettes per day, site (Minneapolis VA vs. others), first-stage randomization (4 vs. 8 week assessment) and second-stage randomized treatment group. In general, adjusted models tend to have higher power (although not guaranteed for a nonlinear model), but the interpretation of the

treatment effect estimate is challenging if there is treatment effect heterogeneity which is not accounted for in the model.² Similar adjusted models will also be the primary analysis for secondary aims 2 and 3. The unadjusted analyses described in the protocol paper will be a secondary analysis.

3. Methods to handle missing data: The SAP in the protocol paper specifies that “We will address missing response data using multiple imputation and additional sensitivity analyses.” Multiple imputation will be done using the full conditional specification with predictive mean matching.^{3 4 5} Covariates included in the imputation include age, gender, cigarettes per day at baseline, time to first cigarette at baseline, site, randomized treatment groups, and seven-day point prevalence at 4, 8, and 12 weeks, 6 months, and 12 months, in addition to 18 month long-term cessation. Note that some of these covariates may be missing as well and the full conditional specification enables one to impute these covariates as well. The imputation models for binary and continuous covariates will use logistic and linear regression models with main effect terms for all the other covariates. Twenty complete datasets will be imputed and the estimates from each the analysis of each complete datasets will combined using Rubin’s combining rules. Participants who died will be recorded as a “failure,” and we will not stochastically impute their endpoint. As a sensitivity analysis, we will also stochastically impute a cessation endpoint for those who died during the study. Note that only the primary endpoint will be imputed, imputation for other secondary endpoints will not be considered. Sensitivity analysis includes assuming those without data are still smoking and complete case analysis. Additional sensitivity analyses which may be considered (which do not assume that the missigness is ignorable) include joint models for longitudinal smoking cessation and nonresponse, pattern mixture models, and selection models.
4. Lung Cancer Screening Results: Secondary aim 4 addresses whether or not lung cancer screening results moderate smoking cessation outcomes. Due to changes in the eligibility criteria, participants may or may not have undergone lung cancer screening at any time during the 1 year of treatment provided by the study. For the purposes of this analysis, we will use the Lung RADS score from the first *screening* CT during the treatment period or just prior to the outreach call (the electronic medical record is queried up to 6 months prior to enrolment). When the Lung RADS score is considered an ordinal measure, those without CT scans will be considered to have a Lung RADS score of 0. As a sensitivity analysis, we will also group those participants with Lung RADS score of 1.

¹ Fu SS, Rothman AJ, Vock DM, et al. Program for lung cancer screening and tobacco cessation: Study protocol of a sequential, multiple assignment, randomized trial. *Contemp Clin Trials*. 2017;60:86-95. doi:10.1016/j.cct.2017.07.002

² FDA (2019). Adjusting for Covariates in Randomized Clinical Trials for Drugs and Biologics with Continuous Outcomes. *Draft Guidance for Industry*.

³ Liu Y, De A. Multiple Imputation by Fully Conditional Specification for Dealing with Missing Data in a Large Epidemiologic Study. *Int J Stat Med Res*. 2015;4(3):287-295. doi:10.6000/1929-6029.2015.04.03.7

⁴ Van Buuren, S. (2007). "Multiple Imputation of Discrete and Continuous Data by Fully Conditional Specification." *Statistical Methods in Medical Research* 16:219–242.

⁵ Van Buuren, S. (2012). *Flexible Imputation of Missing Data*. Boca Raton, FL: Chapman & Hall/CRC.

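### The one verification-based analysis imputes refused and unreturned tests together with kits never sent, and the SAP states no conservative version for verification

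*SAP*

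**What the plan says.** Section 1.3, item 1, changes the primary outcome to self-reported long-term abstinence at Week 78, because COVID-19 stopped saliva collection for part of the sample. One analysis still uses verification: "As a supportive analysis, we will impute the missing biochemical verification data on those self-reporting long-term abstinence". It covers people "who declined biochemical verification, did not return the saliva/iCO smokerlyzer kits, or who were not sent a kit in window". The three groups share one sentence, and none is treated differently.

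Section 1.2.1 explains why some kits were not sent. From March 23 to May 19, 2020, "no participants were sent any biochemical verification", although the study later tried to send iCO devices to those people even when out of window. After that, "We paused sending iCO smokerlyzers from July 2020 to December 2020 due to limited product availability".

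Section 1.3, item 3, sets out the handling of missing response data: "Multiple imputation will be done using the full conditional specification with predictive mean matching", with a list of covariates. That list contains neither the verification result nor the reason it is missing. Item 3 adds: "Note that only the primary endpoint will be imputed, imputation for other secondary endpoints will not be considered". It also says: "Sensitivity analysis includes assuming those without data are still smoking and complete case analysis". Models for non-ignorable missingness are optional.

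**The concern.** The pooled groups differ in why verification is missing. A kit that was not sent because of a calendar date or a supply problem tells us little about whether that person smoked. A person who reports abstinence, is offered a test and then declines or does not return it has made a choice that may depend on smoking. Imputing from tested people with similar covariates assumes that this choice carries no further information.

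Item 3's still-smoking analysis does not clearly reach these people. They gave a self-report, so their primary endpoint is observed and they are not without data in the ordinary sense. The plan therefore commits to a pessimistic bound for missing self-report and states none for missing verification.

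With a self-report primary outcome, the verified analysis is the only stated check on over-reporting. If its assumption is optimistic, the check leans toward the result it is meant to test.

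**Working it through.** **1. The plan's own figure.** Table 3 gives pooled prolonged abstinence at Week 78 as 129/636 = 20.28%, stated as 20.3%. It reproduces. The 129 is a proxy for the group that would be verified. Table 3 also requires its item 4 to be answered No, which the outcome definition in section 1.3 does not, and it pools all 636 rather than the 510 incomplete responders of the primary aim.

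**2. Share of Week 78 dates in a no-kit period.** The documents give enrolment from November 11, 2016 to September 25, 2019 (1,049 days inclusive) and the no-kit dates. Assumption: even enrolment, with Week 78 falling 546 days after enrolment.
- March 23 to May 19, 2020: 57/1,049 = 5.4%.
- July to December 2020: 124 to 184 days, depending on the exact start and end, which the SAP does not give. 124/1,049 = 11.8%; 184/1,049 = 17.5%.
- Total: 181/1,049 = 17.3% to 241/1,049 = 23.0%.

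**3. Self-reported abstainers sent a kit in window.** 129 × (1 − 0.230) = 99 to 129 × (1 − 0.173) = 107.

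**4. Offered but not tested.** Assumed return is 50-80%. Lowest: 99.4 × 0.20 = 19.9. Highest: 106.7 × 0.50 = 53.4.

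**5. Difference between the two rules.** Assume a pass rate of 70-90% among those tested, and that imputation confirms untested people at about that rate.
- Lowest: 19.9 × 0.70 = 13.9 people; 13.9/636 = 2.2 points.
- Highest: 53.4 × 0.90 = 48.0 people; 48.0/636 = 7.6 points.

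**6. Sensitivity to the enrolment pattern.** Section 1.2.1 reports a new site in June 2018 and wider eligibility in September 2018, so even enrolment is doubtful. Suppose the rate doubled from September 1, 2018. The no-kit share becomes 25.2% to 33.5%, 86 to 97 people are sent a kit, and the difference is 1.9 to 6.8 points.

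**7. Sensitivity to late kits.** Under even enrolment, suppose everyone missed from March to May 2020 later received a kit. Only the second gap then counts (11.8-17.5%), 106 to 114 people are offered one, and the difference is 106.4 × 0.20 × 0.70/636 = 2.3 to 113.8 × 0.50 × 0.90/636 = 8.0 points.

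**8. Cross-check by another route.** Let v be the pass rate and r the share of the 129 who declined or did not return a kit. Imputing everyone gives 129 × v verified. Counting refusal and non-return as not verified gives 129 × (1 − r) × v. The difference is 129 × r × v/636. With v = 70% and r = 10% it is 9.0/636 = 1.4 points; with v = 90% and r = 40% it is 46.4/636 = 7.3 points. At v = 80% and r = 30% the two rules give 103.2/636 = 16.2% and 72.2/636 = 11.4%.

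**9. Arm difference.** This needs, for each arm, the number offered a kit and not tested, and the imputed pass rate. The SAP gives neither, so it cannot be computed.

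**The case against.** A reader might infer that untested self-reports are simply counted as verified. The text does not support that: verification is to be imputed, and an imputed value can be a fail.

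A reader might also take a common rule for all three groups as written. It is only the natural reading of one sentence, because no model for verification is given. If item 3's method carries over, it conditions on arm, site, smoking intensity and earlier seven-day abstinence, so it would not hand every refuser one flat pass rate.

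Nor can it be said that the SAP has no conservative analysis at all. Item 3 lists one and does not expressly confine it to missing self-report. What can be said is that none is stated for verification. The protocol paper, which is not at hand, may say how refused tests were to be handled.

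The size rests on assumed return and pass rates, and nothing in the SAP suggests that return differed by arm, so a claim that the treatment contrast is biased would go too far. Counting every refuser as smoking is itself an untestable extreme. The boundary between groups is also not clean, since some people not sent a kit in window were to be sent one late.

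All of this stands, and it limits the claim. It does not remove the core of it. Conditioning on covariates still assumes that refusal is uninformative given those covariates, and nothing stated in this SAP tests that assumption.

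**Conclusion.** The point holds as a weakness in a supportive analysis. The SAP puts refusal, non-return and kits not sent into one imputation step, and states no separate treatment of the first two and no conservative version for verification. The missing-at-random assumption is reasonable for kits not sent for calendar or supply reasons, and probably optimistic for people who were offered a test and not tested.

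The choice could move the pooled verified rate by roughly 2 to 7.5 points of 636, given the assumed return and pass rates. The enrolment pattern and late kits shift the ends of that range somewhat without changing its order. The primary analysis does not change, because self-report is observed for these people.

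Separately, items 1 and 3 of section 1.3 do not fit together: one imputes verification, while the other confines imputation to the primary endpoint, which is now self-report.

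**What to change.** - Keep the present impute-everyone analysis and label it the optimistic bound.
- Add a pre-specified version that imputes verification only for people never offered a kit. Anyone offered a kit at any time, including late and out of window, who declined or did not return it counts as not verified abstinent.
- Write down the imputation model for verification and its predictors.
- Tabulate kits sent, returned, declined and passed by arm.
- Reconcile item 3's limit on imputation with item 1.

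The cost is SAP wording, one table and one more run on data the trial should already hold. Section 1.1 says the SAP was prepared before unblinding, so the rule can be fixed without sight of results; if comparisons have since been seen, the added version should be labelled accordingly. The downside is that the conservative version may undercount true abstainers who did not return a kit. Both versions should therefore be reported as a range.

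### The adjusted primary model omits baseline time to first cigarette without giving a reason, which forgoes a probably small gain in power

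*SAP*

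**What the plan says.** SAP section 1.3, item 2 replaces the unadjusted primary analysis with an adjusted one and gives the motive: "To account for the under-enrolment, the primary analysis for the primary aim" becomes a "logistic regression model with covariates for age, cigarettes per day, site (Minneapolis VA vs. others), first-stage randomization (4 vs. 8 week assessment") and the second-stage arm. It expects some benefit but qualifies it: "adjusted models tend to have higher power (although not guaranteed for a nonlinear model"). The unadjusted analysis is kept as secondary. The same model serves secondary aim 1.

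Item 3 of the same section sets out the multiple imputation: "Covariates included in the imputation include age, gender, cigarettes per day at baseline, time to first cigarette at baseline, site, randomized treatment groups", followed by seven-day abstinence at several follow-up times and the 18-month outcome. It adds: "Note that some of these covariates may be missing as well", and says that the chosen method can impute them too.

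On numbers, item 2 states: "A total of 510 incomplete responders were randomized to second stage treatment". The target had been higher: "Based on the sample size re-estimation we anticipated between 525 and 560 incomplete responders".

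**The concern.** If adjustment is adopted to win back power, the choice of covariates decides how much is won back. Item 3 names five baseline characteristics: age, gender, cigarettes per day, time to first cigarette and site. Item 2 carries three of them into the outcome model. The follow-up abstinence measures in item 3 are rightly kept out, because they come after randomization. That reason does not apply to time to first cigarette, a baseline smoking measure that the authors thought worth using when filling in the endpoint.

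What is at stake is a little power for the primary comparison. Neither the validity of the randomized comparison nor its type I error is affected.

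**Working it through.** **Inputs from the SAP.** There are 510 incomplete responders; by Table 2, TLC 133 + 123 = 256 and TLC + MTM 120 + 134 = 254. Section 1.2.4 expects that "of those incomplete responders between 10-15% would achieve long-term abstinence with TLC alone", and the design effect is a difference of 10 percentage points at 80% power or more.

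**Assumptions, not in the SAP.** Two-sided alpha of 0.05. Time to first cigarette is coded as an early-smoker indicator with 60% prevalence and an odds ratio for abstinence of 0.7, 0.5 or 0.35. Its latent correlation with cigarettes per day is 0 or 0.5. Cigarettes per day has an odds ratio of 0.8 per standard deviation. Outcome data are complete. Age, site and first-stage arm are left out of the working model.

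**Step 1: reproduce Table 4.** With p̄ the mean of the two rates, n per arm and no dropout,

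power = Φ{ [d − 1.96·√(2p̄(1−p̄)/n)] / √[(p₁(1−p₁) + p₂(1−p₂))/n] }.

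| Incomplete responders | 7.5 points, TLC 10% / 15% | 10 points, TLC 10% / 15% |
|---|---|---|
| 560 (Table 4: 73 / 62; 91 / 84) | 73.3 / 62.4 | 91.4 / 84.3 |
| 525 (Table 4: 70 / 60; 90 / 82) | 70.5 / 59.6 | 89.6 / 81.9 |
| 510 (actual, 256 v 254) | 69.2 / 58.4 | 88.8 / 80.8 |

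All eight cells of Table 4 agree within 1 point. The shortfall is 525 − 510 = 15 to 560 − 510 = 50 participants and costs about 1 to 4 points of power (for example 81.9 − 80.8 = 1.1 and 84.3 − 80.8 = 3.5).

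**Step 2: effect of adding the variable.** A large-sample logistic model with treatment and cigarettes per day was fitted with and without time to first cigarette and scaled to 510 participants. With z = log odds ratio / standard error, power = Φ(z − 1.96), and the equivalent extra participants are 510 × [(z with / z without)² − 1]. For a 10-point difference:

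| TLC rate | Assumed OR | Correlation | z without → with | Power without → with | Extra participants |
|---|---|---|---|---|---|
| 15% | 0.7 | 0 | 2.806 → 2.815 | 80.1 → 80.4% | 3.3 |
| 15% | 0.5 | 0 | 2.804 → 2.834 | 80.1 → 80.9% | 11.1 |
| 15% | 0.35 | 0 | 2.801 → 2.868 | 80.0 → 81.8% | 24.6 |
| 15% | 0.35 | 0.5 | 2.829 → 2.888 | 80.7 → 82.3% | 21.8 |
| 10% | 0.7 | 0.5 | 3.122 → 3.130 | 87.7 → 87.9% | 2.5 |
| 10% | 0.5 | 0 | 3.113 → 3.141 | 87.6 → 88.1% | 8.9 |
| 10% | 0.35 | 0 | 3.111 → 3.171 | 87.5 → 88.7% | 19.7 |

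**Step 3: where the gain comes from.** At a 15% TLC rate, OR 0.5 and no correlation, the standard error rises from 0.2282 to 0.2305. The log odds ratio moves from 0.640 to 0.653. The ratio therefore goes from 0.6398/0.2282 = 2.804 to 0.6532/0.2305 = 2.834. The benefit is in power, not in a narrower interval for the log odds ratio.

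**Step 4: simulation check.** With 3,000 trials per setting at a 15% TLC rate and a 10-point difference, the gains were about 0.2 and 0.0 points (OR 0.7, correlation 0 and 0.5), 1.2 and 0.8 points (OR 0.5), and 1.4 and 1.7 points (OR 0.35), with Monte Carlo standard errors of 0.2 to 0.4 point. When the variable was not prognostic (OR 1), the change was 0.0 and −0.1 point, so adding a useless term costs essentially nothing.

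**The case against.** The case for leaving the model alone is respectable. Imputation models are commonly broader than analysis models, because auxiliary variables make the missing-at-random assumption more plausible. Presence on the item 3 list therefore does not show that a variable is prognostic. A reader might infer that items 2 and 3 contradict each other; they do not. Item 2 fixes a closed covariate set before unblinding and keeps the unadjusted analysis, which is sound practice.

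A reader might also infer that the plan gives away free precision. Step 3 shows otherwise for a logistic odds ratio, and item 2 itself warns that a power gain is not assured.

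Nor does the SAP support reading the omission as uncorrected imbalance in dependence. No imbalance is shown, randomization and the standard error already allow for chance imbalance, and cigarettes per day is in the model. The two-level site term and the absence of gender might look like further losses, but the SAP gives no figures on abstinence by site or gender that would show one.

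Finally, the change is not wholly without cost. Item 3 does not say how often baseline values are missing, and a complete-case sensitivity analysis with the same model would lose those participants. Item 3's restriction of imputation to the primary endpoint is made against other secondary endpoints. It does not withdraw the imputation of missing covariates for the main analysis.

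All of this limits the size and wording of the point. It does not explain why the variable is left out of a model chosen to recover power.

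**Conclusion.** The point holds as a minor one about efficiency. The primary model omits a plausible baseline predictor that the trial already has, without explanation, in an analysis adopted to compensate for low enrolment. The likely cost is about 0 to 2 points of power at 510 participants, or about 2 to 25 participants' worth of information, against a shortfall of 15 to 50.

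That range rests wholly on the assumed odds ratios of 0.7 to 0.35, the 60% prevalence, and complete outcome data. The SAP gives neither the variable's prognostic strength nor its correlation with cigarettes per day. If it adds nothing beyond cigarettes per day, the gain is nil. Unadjusted power for the 10-point design effect already stands at 80.8% to 88.8% with complete data, so the trial's adequacy does not turn on this choice.

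**What to change.** Before unblinding, add baseline time to first cigarette to the item 2 model for the primary aim as a single pre-specified term, either binary or an ordinal score. State the coding, since item 3 gives none to copy. Take missing baseline values from the imputations already planned in item 3, and keep the unadjusted analysis as secondary. In secondary aim 1, with 126 participants, add at most this one term.

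The cost is a line of SAP text and one parameter, with no new data. The complete-case sensitivity analysis may drop participants whose value is missing, and the report should state how many.

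### The 18-month endpoint is imputed with main effects only and without Lung-RADS; if secondary aim 4 uses that imputed endpoint, its Lung-RADS terms are modestly distorted, mostly toward zero

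*SAP*

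**What the plan says.** Section 1.3 item 3 imputes the 18-month cessation endpoint by fully conditional specification with 20 imputations. The listed variables are age, gender, two baseline smoking measures, site, the randomized groups and smoking status at five earlier times. Lung-RADS is not listed. The model form is stated: "The imputation models for binary and continuous covariates will use logistic and linear regression models with main effect terms for all the other covariates". On scope, item 3 says "Note that only the primary endpoint will be imputed, imputation for other secondary endpoints will not be considered". On alternatives it says "Sensitivity analysis includes assuming those without data are still smoking and complete case analysis". Deaths count as failures and are not imputed in the main analysis.

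Item 4 says "Secondary aim 4 addresses whether or not lung cancer screening results moderate smoking cessation outcomes". It then fixes the coding: on the ordinal scale "those without CT scans will be considered to have a Lung RADS score of 0", followed by "As a sensitivity analysis, we will also group those participants with Lung RADS score of 1", which I read as placing the no-CT group with score 1. It does not say which cessation outcome aim 4 uses or how missing values are handled there.

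Item 2 re-specifies the analysis models for the primary aim and secondary aim 1, then adds "Similar adjusted models will also be the primary analysis for secondary aims 2 and 3". It does not mention aim 4.

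Section 1.2.3 gives the amount of missing data: "data are available on 86.8% (547/630) and 84.6% (529/625) of participants at Week 52 and Week 78".

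**The concern.** An imputation model should contain the terms that the analysis will estimate. If it leaves out the moderator, the imputed outcomes carry no moderation except what the earlier smoking measures pass on. Mixing them with observed outcomes dilutes the Lung-RADS terms. Adding Lung-RADS as a main effect would not cure an interaction analysis, because the main-effects rule still excludes the product with treatment. The variable list is introduced in a way that may not be exhaustive, so Lung-RADS could be added later, but the rule on model form would still bind.

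At stake is the reading of aim 4. A null result could partly reflect the imputation, and two analysts following the SAP could run aim 4 on different data.

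**Working it through.** **Share imputed (section 1.2.3, Table 1).** Data available at Week 78: 494 + 35 = 529. Alive: 636 − 11 = 625. 529/625 = 84.6%, as the SAP states. Alive without data: 77 + 16 + 3 = 96, and 96/625 = 15.4%. As a check, 96 + 11 deaths = 107, the missing count for past-7-day smoking in Table 3. The SAP does not split the 96 by responder group or arm.

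**Assumed inputs.** The SAP gives no Lung-RADS distribution, no effect sizes and no link between interim and final abstinence. I assume logit P(abstinent) = −1.9 + 0.4t + b·t·m, where t is second-stage treatment and m is Lung-RADS positive (yes/no), with b = 0.5 or 1.0 and P(m=1) = 0.15 or 0.30. Data are missing completely at random unless stated.

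**Worked case, no help from interim data (b = 1.0, P(m=1) = 0.30).**
- True probabilities in the treated arm: expit(−1.5) = 0.1824 for m=0 and expit(−0.5) = 0.3775 for m=1.
- Imputing without m gives both groups 0.70 × 0.1824 + 0.30 × 0.3775 = 0.241.
- Completed data, m=0: 0.8464 × 0.1824 + 0.1536 × 0.241 = 0.1914, logit −1.441.
- Completed data, m=1: 0.8464 × 0.3775 + 0.1536 × 0.241 = 0.3566, logit −0.590.
- Lung-RADS has no effect in the control arm here, so the recovered interaction is −0.590 + 1.441 = 0.851 against a true 1.00, a loss of 15%.

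Across the four combinations of b and P(m=1) the ratio is 0.851 to 0.860.

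**With the five interim measures in the model.** I assume two sets of P(abstinent at visit | final success)/P(abstinent at visit | final failure) at weeks 4, 8, 12 and months 6, 12:
- strong: .30/.08, .35/.10, .50/.15, .70/.18, .85/.20
- weak: .20/.08, .22/.10, .30/.15, .45/.20, .70/.25

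Exact large-sample ratio of completed-data to true interaction, interim data fully observed:

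| Imputation model | Ratio |
|---|---|
| As in the SAP | 0.89 to 0.94 |
| Lung-RADS main effect added | 0.88 to 0.93 |
| Lung-RADS and its product with treatment added | 1.000 |

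If some of the 96 also lack the 12-month measure (15 to 83 of them), the SAP model gives 0.872 to 0.937. If interim abstinence carries none of the Lung-RADS effect, it gives 0.830 to 0.862 over a wider set of inputs. If aim 4 only tests association of Lung-RADS with cessation, the SAP model gives 0.869 to 0.936, and adding Lung-RADS restores 1.000.

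**Independent recomputation with other assumed inputs** (large simulated samples; binary and 0–4 ordinal Lung-RADS; one 12-month predictor of varying strength). The interaction ratio was 0.834 to 0.924 with data missing completely at random. It fell to 0.799 when missingness was 1.6 times as frequent in Lung-RADS positives and there was no interim predictor. Complete-case estimates in the same runs showed no material bias (0.700 against 0.704, for example).

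Together, shrinkage is about 6 to 17% under missing completely at random, and reaches 20% when missingness also rises with Lung-RADS.

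**Missingness differing by arm.** With b = 0, a Lung-RADS main effect of ±0.5 to ±1.0, and 10% against 20.8% missing by arm (assumed), the SAP model with interim measures gives a false interaction log-OR of about 0.02 to 0.12 in size. Its sign depends on which arm loses more data.

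**Predictive mean matching**, which item 3 also names, did not change the picture: in simulation the mean estimate was 0.87 (weak set) and 0.93 (strong set) of the full-data value, as with logistic draws.

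**The case against.** The SAP is an update. It refers to a protocol paper for the detailed plan, and item 4 only revises the source and coding of Lung-RADS. The aim 4 model, outcome and analysis set may be specified there, so their absence here is not in itself a fault. Item 4 also speaks of cessation outcomes in general, and only the primary endpoint is imputed. If aim 4 uses other outcomes or observed data, there is no problem. If item 3 does extend to aim 4, so does its complete-case sensitivity analysis, which is nearly unbiased in the runs above.

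Much of this stands, and it is why the point is conditional and minor. It does not remove the point. Item 3 addresses missing response data in general and makes complete case only a sensitivity analysis, so the imputed endpoint is the likelier basis for aim 4. The restriction to the primary endpoint does not settle the matter, because a secondary aim can use the primary endpoint. The rule that excludes product terms is stated in this document, not left elsewhere.

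A reader might infer three stronger things:
- **That the primary comparison is biased.** The documents do not support this: randomized groups are in the imputation model and the primary model has no Lung-RADS term.
- **That aim 4 will be biased.** This holds only on the inferred reading.
- **That the effect is always conservative and cannot create moderation.** That is true only where missingness does not differ by arm.

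**Conclusion.** The point holds in conditional form and is minor. If aim 4 uses the imputed primary endpoint, 15.4% of living participants contribute outcomes generated without the moderator, and the Lung-RADS terms lose roughly 6 to 20% on the log-odds scale. The loss is smallest when interim abstinence predicts the endpoint strongly. With differential missingness by arm and a prognostic Lung-RADS, a false interaction of up to about 0.12 in log-OR is possible. Only the 15.4% comes from the SAP; Lung-RADS frequency, effect sizes, interim associations and the missingness mechanism are assumed.

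For illustration only: one simulated scenario (n = 510, b = 1.0, 30% positive) gave power of 33% against 44% with the added terms (weak interim set) and 43% against 48% (strong set). Full-data power was 50 to 52% and complete-case power 44 to 45%. A binary 30% split is not the SAP's ordinal coding, so these figures should not be quoted as the trial's power.

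**What to change.** State the aim 4 outcome and its missing-data method, and take one of two routes.

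1. Analyse observed endpoints for aim 4. The issue then disappears.
2. If the imputed endpoint is used, add Lung-RADS to the aim 4 imputation model in the coding(s) that aim 4 analyses. An ordinal score (no CT = 0) plus a no-CT indicator covers both codings in item 4, since grouping no CT with score 1 equals the ordinal score plus that indicator. If Lung-RADS is also analysed in categories, impute with those categories. If aim 4 tests moderation of a treatment effect, add the product of each term with second-stage treatment, or impute by second-stage arm. Report the planned complete-case analysis alongside.

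Cost: one or two sentences, up to four model terms and no new data. Estimates become somewhat more variable (illustrative RMSE 0.54 to 0.58 against 0.50). The terms may be unstable among the 126 complete responders (34 + 28 = 62 TLC-Q, 32 + 32 = 64 TLC-M); use observed endpoints there. If the primary-aim imputation stays as written, the SAP must say which imputed dataset serves which aim.
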